**MEND (Mild Encephalopathy in the Newborn treated with Darbepoetin)**

11.18.2020

Evaluation	Screening	Pre-Entry (Prior to 24 hrs)	Entry (<24 hr of age)	discharge, transfer, or 96 hours of age (which ever occurs first)	3-10 days	Discharge	4 months corrected age	8-12 months corrected age
Screen admissions to NICU	X	X						
Documentation of Gestational Age		X						
Informed Consent		X						
Maternal Demographics and History			X			X		
Blood Pressure			X		X	X		X
Modified Sarnat Exam				X				
MRI as available from clinical care					X	X		
Hematology (CBC/transfusions/phlebotomy loss) as available from clinical care			X			X		X
Administration of study drug IV			X					
Liver/kidney Function Tests (as clinically available)					X			
Complete Physical Exam including weight, head circumference and length			X			X		
Telephone contact to review current status							X	
Ages and Stages phone questionnaire							X	
Phone/in person survey on hospitalizations, seizures, need for respiratory support, failure to thrive, medication use, use of early intervention, hearing impairment, concerns with vision							X	X
Neurodevelopmental assessment Bayley III & Standardized Neurologic exam								X
Weight, length, head circumference, blood Blood pressure, and heart rate								X

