### 3. Study Design

Eligible patients will be identified by the admitting neonatologist or by the research nurses based on admission diagnosis (perinatal depression, perinatal acidemia, HIE or NE, encephalopathy, clinical assessment for the need for therapeutic hypothermia).

**Inclusion Criteria:** Infants will be eligible for the MEND trial if they have a gestational age  $\geq$  34 weeks by best obstetric estimate, are <24 hours old and have evidence of mild encephalopathy and **DO NOT** have moderate-severe acute NE as defined by Shankaran et al based on a modified Sarnat examination performed at <6 hours of age (48).

Eligibility will include criteria presently used in the NICU to initiate therapeutic hypothermia and used in the NICHD NRN hypothermia trial:

- 1) History of an acute perinatal event (abruption, cord prolapsed, severe fetal heart rate abnormality, or meconium staining)
- 2) Infant is evaluated for hypothermia therapy and **DOES NOT** meet clinical criteria for TH.
- 3) Infant has an IV for clinical treatment

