### Exclusion Criteria

- 1) Moderate/Severe encephalopathy on modified Sarnat examination at < 6 hours of age
- 2) Major congenital and/or chromosomal abnormalities
- 3) Prenatal diagnosis of brain abnormality or hydrocephalus
- 4) Severe growth restriction ( $\leq$  3% for gestational age)
- 5) Central venous hematocrit >65%, platelet count >600,000/dL, and/or neutropenia (ANC<500  $\mu$ L)
- 6) ECMO
- 7) Infant judged critically ill and unlikely to benefit from neonatal intensive care by the attending neonatologist

After eligibility is confirmed, with approval from the Attending Care Provider, the parent or legal guardian will be approached for consent (as noted below under consent process). All patients eligible for this study will be managed in the NICU.

**Drug administration:** Each center will obtain their own Darbe through their research pharmacies. Randomization will take place at each site using a provided block-design randomization table created by UNM research pharmacy. The site pharmacy will then dispense the study drug to the research nurse in a closed container. Darbe and vehicle are the same in appearance, and will be labeled “study drug”.

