#### **Data collection**

At study entry maternal demographics, specifically: age, education, race, ethnicity will be collected. A modified Sarnat exam will be repeated at discharge, transfer, or 96 hours of age (which ever occurs first) and documented. We will collect vital signs, MRI, hemoglobin/hematocrit, CBC with differential, liver function tests, and complete physical exam if they are done as indicated by clinical care. MRIs done for clinical indication will be de-identified and sent to a pediatric neuroradiologist for a centralized read. Once de-identified, these will be sent via CD or Lifelimages to UT Southwestern where they will be read by the neuroradiologist. We are requesting waiver of consent to send de-identified MRIs to UT Southwestern for an additional reading. All MRIs have been and will be ordered per clinical indication and are not required under the study protocol.

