### **5. Data Analysis**

This will be a multicenter pilot/feasibility trial to assess Darbe for infants who do not qualify for TH. Data from this trial will be used to power a large multicenter RCT. Primary outcome variable will be the incidence of abnormal neurodevelopmental score by Bayley III <85 or GMFS of >1 at 8-12 months of age. Chi-square or Fisher exact statistical tests will be performed for all categorical values. For continuous variables, t tests will be performed. All outcomes will be analyzed based on intention to treat inclusion of all randomized patients. We estimate infants who received Darbe will experience an estimated 30% decrease in neurodevelopmental impairment, defined as BSID III cognitive score or motor score <85, or a Gross Motor Function Classification Scale score >1. A total of 40 infants per group will be required to identify a 30% difference between groups.

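### The modified Sarnat exam before 6 hours, on which eligibility rests, is not named as study data or used in the analysis, and mild encephalopathy has no operational definition

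*Combined protocol and SAP*

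**What the plan says.** **Eligibility.** The lead-in to the inclusion criteria (section 3, Study Design) admits infants who "are <24 hours old and have evidence of mild encephalopathy and" do not have moderate-severe encephalopathy under a cited definition, "based on a modified Sarnat examination performed at <6 hours of age". Three numbered items follow: a perinatal event, evaluation for hypothermia without meeting its criteria, and an IV in place. The first exclusion is "Moderate/Severe encephalopathy on modified Sarnat examination at < 6 hours of age".

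**Data capture.** Under Data collection: "At study entry maternal demographics, specifically: age, education, race, ethnicity will be collected". On the exam itself: "A modified Sarnat exam will be repeated at discharge, transfer, or 96 hours of age (which ever occurs first) and documented". The research-procedure list (Standard of Care vs. Research-Related Procedures) names a neurological exam at that later time only. In the schedule of evaluations, the row "Modified Sarnat Exam" has one mark, in the column for discharge, transfer or 96 hours. Screening, Pre-Entry and Entry are blank in that row, although other rows carry pre-dose or entry marks (gestational age, consent, blood pressure, physical exam).

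**Analysis.** Section 5 states: "Chi-square or Fisher exact statistical tests will be performed for all categorical values". It names no covariate and no baseline severity variable.

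**The concern.** Neurological status before dosing is a natural prognostic factor in this population, and every infant must be examined for it to be eligible. The Sarnat exam that the plan does schedule falls, in the ordinary course, after dosing, so it cannot serve as a baseline. Followed as written, the specified dataset lacks the one pre-dose severity measure already being taken.

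Three things are at stake. The report may be unable to show how severe the enrolled infants were, or whether the arms were alike on severity. The primary comparison gives up whatever precision adjustment would bring. And seven named centers may apply an undefined threshold for mild differently. The last matters beyond this trial, because section 5 says its data will be used to power a larger one, and a control rate from an uncertain mix of infants is a poor basis for that.

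**Working it through.** **1. Is the early exam specified as data?**

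| Place | Exam before 6 hours | Later exam |
|---|---|---|
| Inclusion lead-in and exclusion 1 | Used for eligibility | – |
| Data collection | Implied by the word for repetition; not listed | To be documented |
| Research-procedure list | Not listed | Listed |
| Schedule of evaluations | No mark | Marked |
| Section 5, Data Analysis | Not used | Not used |

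The three places that specify data agree with one another, so a table-extraction fault is an unlikely explanation.

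**2. Is mild defined?** The lead-in requires that infants "have evidence of mild encephalopathy" but gives no grade, count or form. The cited definition and the exclusion both concern moderate-severe disease. The numbered items require no abnormal finding. A normal exam is therefore excluded by one undefined phrase and by nothing countable.

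**3. The plan's own figure.** Section 5 gives 40 per group for a 30% difference, without alpha, power or control rate, so it cannot be strictly reproduced. Assuming two-sided 0.05, 80% power and an absolute 30 points,

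n = [1.96√(2p̄(1−p̄)) + 0.84√(p₁(1−p₁) + p₂(1−p₂))]² / (p₁−p₂)²

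gives 39 per arm for 50% vs 20%, 41 for 55% vs 25%, 42 for 60% vs 30%, and 28 for 36% vs 6%. Read as a relative 30% reduction, it gives 285 per arm at a 36% control rate and 170 at 50%. The figure of 40 fits an absolute difference from a control rate near 50%. I use that, and 36% vs 6%, as two assumed cases. The 36% is the short-term abnormality figure in section 2, Background, not a Bayley rate.

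**4. Dilution if normal-exam infants did enter (all rates assumed).** With a share f of normal-exam infants and 10% impairment in both arms, each arm's rate becomes (1−f)p + 0.10f. At f = 0.20:

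- 50% becomes 0.8×0.50 + 0.2×0.10 = 42%, and 20% becomes 0.8×0.20 + 0.2×0.10 = 18%. Exact power of the uncorrected chi-square at 40 per arm falls from 82% to 66%; with Fisher's test it falls from 75% to 57%.
- 36% becomes 30.8%, and 6% becomes 6.8%. Chi-square power falls from 94% to 83%.
- At f = 0.05 in the 50% vs 20% case, chi-square power is 78%.

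The 36% vs 6% case is slightly strained, since it gives treated mild infants a lower rate than normal-exam infants.

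**5. Chance imbalance.** For a factor present in half the infants, a gap above 15 points means the arms differ by more than 0.15×40 = 6 infants. With two independent binomials (40, 0.5), that has exact probability 14.6%. The normal approximation, with SD √(2×0.25/40) = 0.112, gives 18% because it ignores discreteness; the exact value is the one to use. If the more abnormal half carried 30 points more impairment (assumed), a 15-point imbalance would move the unadjusted difference by 0.15×30 = 4.5 points. The standard error of that difference at 50% vs 20% is √(0.25/40 + 0.16/40) = 0.101, or about 10 points.

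**6. How much adjustment the data can carry.** At 50% vs 20% there are about 40×0.5 + 40×0.2 = 28 events. Treatment plus one severity term gives 28/2 = 14 events per parameter. Adding six indicators for seven centers gives 28/8 = 3.5, which is too thin.

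**The case against.** The strongest reply is that the exam is not lost. It must be done for eligibility, and the Data collection text speaks of the later one as a repeat. Section 4 (Prior Approvals) requires case histories of all pertinent observations, and section 17 (Data Management/Confidentiality) allows study data to be taken from the electronic record. Section 15 (Consent Process) mentions a study entry form that is not in the documents and could hold a field for it. All of this stands. A reader might infer that entry severity cannot be verified or adjusted for; the documents do not support that. They show only that capture and use are unspecified. Unspecified retrieval may, however, yield a clinical impression at one center and item scores at another.

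A reader might also infer that normal-exam infants are freely admitted because they pass every numbered item. That is not supported either, since the lead-in sits under the inclusion heading and is binding. The remaining defect is the missing definition and the absence of a specified, recorded check.

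Third, chance imbalance is already covered by the type I error of the randomized test, and the illustrative 4.5-point shift is under half a standard error. That is correct, and the unadjusted test remains valid. Nothing in the documents suggests that 20% of enrolled infants would have normal exams.

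**Conclusion.** The point holds as a gap in specification. The plan rests eligibility on an exam that it does not list as data, plans no use of it, and defines moderate-severe but not mild encephalopathy. It is worth correcting because the measurement is already made and the trial's stated population depends on it.

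It does not bias the randomized comparison and does not invalidate the primary test. Its practical size is uncertain. The power losses in the working (82% to 66%, or 94% to 83%) depend on assumed event rates and on an assumed 20% share of normal-exam infants, and at a 5% share the first loss is only to 78%. The chance of a severity imbalance above 15 points is about 15% if half the infants have the factor. The most secure gain is being able to say which infants were enrolled.

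**What to change.** - Mark the modified Sarnat exam under Screening/Pre-Entry in the schedule of evaluations. Record the time and each category score from the eligibility exam before 6 hours, and list it under Data collection.
- Report these scores by arm in the baseline table.
- In section 5, pre-specify a comparison of the primary outcome adjusted for baseline severity (number of abnormal categories) as a single covariate, without site terms. Report it as a standardized risk difference with a 95% confidence interval alongside the unadjusted chi-square or Fisher test.
- Have the investigators reconcile the lead-in requirement for mild encephalopathy with the numbered criteria and state their own definition of mild. That threshold is a clinical matter for them.

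The cost is one schedule mark, one case report form field (time and category scores) and one covariate, plus the agreed definition. No infant undergoes anything extra.

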#### 4. Prior Approvals

- [name] holds the IND (IND 132207) for this trial.
- See the attached departmental review form.

**Study Resources:** Trained NICU research nurses are available at the University of New Mexico, the University of Utah, and Primary Children's Medical Center NICU's. All sites have a locked office with locking cabinets in which study data will be kept. All participating infants will be assigned a study number and identified for study purposes by that number only.

- All sites have the most current version of the protocol, consent document, and HIPAA authorization.
- We are seeking approval from the IRB's at each site, when obtained they will be added to this document as a modification.
- All modifications will be communicated to sites, and approved (including approval by the site's IRB of record) before the modification is implemented.
- All engaged participating sites will safeguard data as required by local information security policies as they are all actively involved in neonatal clinical trials.
- All local site investigators will conduct the study appropriately.
- *All non-compliance with the study protocol or applicable requirements will be reported in accordance with local policy.*

**Control of Investigational Devices/Drugs:** The study drug will be stored in, controlled and dispensed by, the Investigational Research Pharmacy. Labeling for the study drug will be done per standard investigational drug guidelines employed by the research pharmacy

[name], the sponsor-investigator, will maintain complete and accurate records showing any financial interest in 54.4(a)(3)(i), (a)(3)(ii), (a)(3)(iii), and (a)(3)(iv) of the CFR paid to clinical investigators by the sponsor of the covered study. [name], the sponsor-investigator, will also maintain complete and accurate records concerning all other financial interests of investigators subject to part 54 of the CFR.

[name] and qualified study team members will prepare and maintain adequate and accurate case histories that record all observations and other data pertinent to the investigation on each participant who is given darbepoetin or employed as a control in the study. [name] and the Clinical Research manager, will be responsible for preparing and maintaining these case history reports at the University of New Mexico.

[name] or her designee will retain the records and reports required by 21 CFR 312.57 (c) for two years after a marketing application is approved for the drug; or if the application is not approved for the drug, until 2 years after shipment and delivery of the drug for investigational use is discontinued and FDA has been so notified.

## **MEND (Mild Encephalopathy in the Newborn treated with Darbepoetin)**

11.18.2020

[name] will ensure that reserve samples and/or lot numbers of the study drug, darbe will be maintained at the University of New Mexico and released to the FDA upon request, in accordance with, and for the period specified in section 320.38. These study drug samples will be maintained in a -80 freezer at the University of New Mexico for later testing for pK analysis.

### **Assurance of IRB Review:**

[name] and participating clinical investigators will promptly report to reviewing IRBs all unanticipated problems involving risk to human participants or others according to IRB policy. [name] and/or study staff will be responsible for preparing and submitting these reports to the University of New Mexico IRB and maintaining files of IRB approvals/acknowledgements.

### **5. Data Analysis**

This will be a multicenter pilot/feasibility trial to assess Darbe for infants who do not qualify for TH. Data from this trial will be used to power a large multicenter RCT. Primary outcome variable will be the incidence of abnormal neurodevelopmental score by Bayley III <85 or GMFS of >1 at 8-12 months of age. Chi-square or Fisher exact statistical tests will be performed for all categorical values. For continuous variables, t tests will be performed. All outcomes will be analyzed based on intention to treat inclusion of all randomized patients. We estimate infants who received Darbe will experience an estimated 30% decrease in neurodevelopmental impairment, defined as BSID III cognitive score or motor score <85, or a Gross Motor Function Classification Scale score >1. A total of 40 infants per group will be required to identify a 30% difference between groups.

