#### PK Sampling

Blood samples will be used to establish population pharmacokinetics. Scavenged blood samples of 0.05 mL of blood will be collected from all clinical blood draws throughout the infant’s hospitalization and sent to the University of Iowa for population pharmacokinetics using meso-scale discovery assay to detect Epo levels. Since a baseline sample is also required for immunogenicity testing we will collect an extra 0.3 mL of blood with the “pre-drug” blood work drawn in the NICU. Study participants will have the option of opting in for this additional blood draw. This will ensure that there is enough blood for potential immunogenicity testing and pK analysis. Every effort will be made to obtain this sample with a blood draw that is needed for clinical purposes (such as a glucose check). All other pk samples will be off of scavenged blood. Parents will be given the option to opt into this part of the study on the consent form.

Parents of participants will be contacted by phone call at 4 months of age which will include developmental screening via a modified Ages and Stages questionnaire (attached), number of hospitalizations, seizures, need for assisted respiratory support, failure to thrive, medication use, use of early intervention services, hearing impairment, any concern with vision.

Participants will have neurodevelopmental testing (Bayley III and Gross Motor Function Assessment) performed at 8-12 months of age. We will also conduct a brief medical exam including weight, length, head circumference, blood pressure, and heart rate.

In addition, we may contact the child’s primary care provider and ask for the baby’s most recent medical history and the result of the most recent hematocrit.

Data will be kept for analysis for up to 10 years.

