#### **Standard of Care vs. Research-Related Procedures:**

Research-Related procedures:

1. Study drug can be given as soon as the infant is found to **NOT** qualify for TH but before 24 hours of age.
2. Extra 0.3 mL of blood drawn prior to drug administration (optional)
3. Neurological examination at discharge, transfer, or 96 hours of age (which ever occurs first)
4. Follow up phone calls at 4 months of age
5. Bayley Scales of Infant Development examination at 8-12 months corrected age.
- 6.

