## **MEND (Mild Encephalopathy in the Newborn treated with Darbepoetin)**

11.18.2020

7. Weight, length, head circumference, heart rate, and blood pressure at 8-12 months.
8. Medical records from primary care provider including hemoglobin and hematocrit if available when indicated.

Standard of Care:

1. Monitoring and routine supportive care.

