### **Safety**

For the purpose of this study, an **adverse event** (AE) will be defined as any adverse change from the patient's baseline condition that occurred following the administration of the study drug through the end of the study period. Safety will be evaluated during the first 7 days of life or until hospital discharge (whichever comes first) by documenting potential adverse events such as (but not limited to) alterations in blood pressure, secondary infections, neutropenia, thrombotic/vascular events, hematologic events (platelets, Hct level, polycythemia), and hepatic/renal function that are outside of normal range for the study population.

We will assess for the rare complication (1 in 10,000 in adults with renal failure) of pure red blood cell aplasia. The vast majority of babies admitted to the NICU have a CBC with diff drawn on admission. If there is at least 0.5mL of blood remaining (scavenged blood) after analysis, we will collect that blood and use as our baseline sample. Similarly, most babies admitted to the NICU have electrolytes or bilirubin levels drawn at 24-72 hours of age, if there is at least 0.5mL of blood remaining (scavenged blood) after analysis, we will collect that blood and use as our second sample. If the baby remains in the NICU for 2 weeks (uncommon) and has a blood test done for clinical reasons, we will attempt to keep 0.5mL (scavenged blood) to assess for pure blood cell aplasia. Additionally, a letter (attached) will be given to the PCP stating that the patient is enrolled in a research study. If there are concerns for anemia and the PCP orders a CBC within the first year of life we will ask for 0.5mL of blood (scavenged blood). We will ask the lab to hold "scavenged" blood and store for up to 6 months beyond enrollment of the last patient.

We will also ask for the medical records from the child's primary care provider and their most recent hematocrit/hemoglobin.

**Long Term Safety** will involve phone calls at 4 months of age which will include developmental screening via Ages and Stages questionnaire, hospitalizations, seizures, need for assisted respiratory support, failure to thrive, medication use, use of early intervention services, hearing impairment, any concern with vision. In addition we will contact the child's primary care provider and ask for the child's medical records and most recent hematocrit/hemoglobin to assess for safety.

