## **9. Potential Benefits to Subjects**

A potential benefit maybe improved neurodevelopmental outcome due to improved neuronal recovery from the administration of Darbe. In addition, subjects will receive close developmental follow-up via phone calls and exam at 8-12 months of age.

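### Does the mixed use of age and corrected age for the 8-12 month visit leave the primary outcome undefined?

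*Combined protocol and SAP*

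**What the plan says.** Section 5 (Data Analysis) of the combined protocol and SAP gives the outcome as follows: "Primary outcome variable will be the incidence of abnormal neurodevelopmental score by Bayley III <85 or GMFS of >1 at 8-12 months of age". Later in the same paragraph, the sample-size sentence spells out impairment as "defined as BSID III cognitive score or motor score <85, or a Gross Motor Function Classification Scale score >1".

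Section 3 describes the visit in several places:

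- The follow-up text under PK Sampling: "Participants will have neurodevelopmental testing (Bayley III and Gross Motor Function Assessment) performed at 8-12 months of age".
- Item 5 of the research-procedure list (Standard of Care vs. Research-Related Procedures): "Bayley Scales of Infant Development examination at 8-12 months corrected age".
- Item 7 of that list gives no age basis: "Weight, length, head circumference, heart rate, and blood pressure at 8-12 months".
- The schedule of evaluations heads the visit column in corrected age. Its neurodevelopmental row names the Bayley III and a standardized neurologic examination.

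Section 9 (Potential Benefits to Subjects) says that "subjects will receive close developmental follow-up via phone calls and exam at 8-12 months of age".

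The 4-month contact shows the same variation. Item 4 of the list reads "Follow up phone calls at 4 months of age", and the Safety text says long-term safety "will involve phone calls at 4 months of age". The schedule heads that column in corrected age.

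**The concern.** The primary outcome is a yes/no event with a fixed cut-off of 85, so the age at testing, and the age used to turn performance into a score, can decide which side of the line an infant falls on. Eligibility starts at 34 weeks, which makes chronological and corrected age different quantities for some participants. If one center booked visits by one clock and another center by the other, the same event would not mean quite the same thing everywhere. Section 5 intends these data to power a larger trial, so consistency across centers has value.

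The second worry is the gross-motor part. A score above 1 is an event in its own right, yet the schedule row does not list the scale. A site working only from the schedule might leave it out. An infant with a cognitive or motor score below 85 would still count as an event. An infant with both scores at or above 85 and no gross-motor score could not be classed as event-free.

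**Working it through.** **Age basis: size of the difference.** The plan gives no figure here beyond the window of 8 to 12 months, which is 4 months wide. The sample size of 40 per group takes no age as an input and is unaffected.

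Inputs: lowest gestational age 34 weeks (Section 3, Inclusion Criteria); term 40 weeks (assumption); weeks per month = 365.25 / 12 / 7 = 4.348.

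Formulas: offset = (40 − gestational age) / 4.348 months; shared part of the windows = (4 − offset) / 4.

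| Gestational age (weeks) | Offset (months) | Windows share |
|---|---|---|
| 34 | 6 / 4.348 = 1.38 | 2.62 / 4 = 66% |
| 35 | 1.15 | 71% |
| 36 | 0.92 | 77% |
| 37 | 0.69 | 83% |
| 38 | 0.46 | 89% |
| 39 | 0.23 | 94% |
| 40 | 0 | 100% |

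For the extreme infant, born at 34 weeks:

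- The window in chronological age is 8 − 1.38 = 6.6 to 12 − 1.38 = 10.6 months corrected.
- The window in corrected age is 8 + 1.38 = 9.4 to 12 + 1.38 = 13.4 months of chronological age.
- A visit between 9.4 and 12 months of chronological age satisfies both readings.
- The offset is 1.38 / 4, about a third of the window that the protocol already accepts.

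If age is corrected only below 37 weeks (a second assumption; the documents do not say), the offset is zero from 37 weeks on.

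**Age basis: which text governs.** The item that lists the Bayley as a research procedure and the column heading of the schedule are what a coordinator books from, and both use corrected age. The other places give an age without qualification. None says chronological or postnatal, so they are less specific and do not state an opposing rule. Section 9 is a statement of benefits and schedules nothing.

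**Scoring age.** No section states it. Once the visit is dated in corrected age, scoring on the same basis is the natural reading, though this is an inference. The schedule documents gestational age before entry, so corrected age can be computed for every infant. One rule can then be applied to the pooled data, provided raw scores are kept (an assumption).

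**Effect on the comparison.** Infants are randomized at each site from a block table, and treatment is blinded. The age basis depends on gestation, visit date and site practice, none of which depends on the arm. The proportion scoring below 85 under each basis cannot be computed, because the documents give neither a score distribution nor a gestational-age mix.

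**Gross-motor part.** Three places, side by side:

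- The follow-up text defines the testing at this visit as the Bayley III plus a gross-motor assessment.
- Section 5 gives the scale and its threshold.
- The schedule row is labelled as the neurodevelopmental assessment, which is the same activity, and can be read through the follow-up text.

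Section 4 (Study Resources) says every site holds the current protocol, so no site should be working from the schedule alone. The procedure list settles nothing either way, because its item 6 is blank in the text as read. The abbreviation and the full name in Section 5 share a paragraph and a threshold, so they plainly mean one scale.

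**Which Bayley score.** The outcome sentence does not say, but the sample-size sentence in the same paragraph does: cognitive or motor.

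**The case for a change.** The best case for a change is that this is the primary outcome and the texts do differ. Items 4 and 5 of one list use both forms on adjacent lines, which makes it harder to call the unqualified form mere shorthand. Section 15 describes participants as aged 0 to 12 months, and Section 7 puts follow-up between 4 and 12 months. Yet 12 months corrected is 13.4 months of chronological age for an infant born at 34 weeks. Aligning the visit wording would still leave the scoring age open, and a fixed cut-off is sensitive to it: 1.38 months is 1.38 / 8 = 17% of age at 8 months and 1.38 / 12 = 11.5% at 12 months. Seven centers are involved, and the correction would be cheap.

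The textual observations stand. The wording is uneven, the scoring age is unstated, and the upper age in Sections 7 and 15 does not sit exactly with corrected age for the earliest-born infants. What is missing is a consequence. Even this case claims no difference between arms, no inflation of false positives, no shift in the event rate and no count of lost gross-motor scores. The 17% applies only to an infant born at 34 weeks and seen at the very start of the window, and the number of such infants is unknown.

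**Conclusion.** No change to the plan is called for. The age wording is a difference in specificity, and the passages used for booking agree on corrected age. The scoring age is a gap that can be filled with one rule applied to all infants. The absent schedule label is clerical, because the assessment is planned elsewhere for the same visit. At its largest the age difference is 1.4 months with 66% of the window shared, at 34 weeks; it shrinks to zero at 40 weeks, or at 37 if correction stops there. The sample size is unaffected, and no bias between arms follows.

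This rests on a 40-week term, on sites booking from the procedure list and the schedule, and on sites reading the follow-up text as well as the table. The late-preterm share is not given, so an effect on the overall event rate is neither shown nor excluded. Any such effect would fall on both arms alike.
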